4.3.2 Body weight

Body weight will be measured to the nearest 100g in light clothing without shoes using approved calibrated scales. The scale will be placed on a hard, flat surface. Weight will be measured at all appointments.

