4.3.6 Capillary blood glucose measurement

Capillary blood glucose measurement will be performed by the researcher or by the patient witnessed by the researcher. The glucose test strip will be prepared by inserting into a meter without touching the sensor tip and the lancing device will be primed to no more than 2.0mmprick. Prior to measurement, the hands will be washed with warm water and soap and dried thoroughly and the arm dropped to the side to encourage blood flow. The edge of the finger will be pricked and after five seconds the blood droplet will be wiped away with the second droplet used for analysis. Downward pressure may need to be applied to assist with blood flow. Capillary blood glucose will be measured at all appointments.

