4.3.8 Questionnaires

Quality of Life (EQ-5D), Binge Eating and Food Acceptability Questionnaires will be administered electronically at Appt 2 (Baseline), Appt 9 (End of the VLED) and Appt 20 (Week 52).

Questionnaires will be self-completed at the end of the specific appointment.

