4.6 Study schedule

Eligibility for the study and reintroduction of blood glucose lowering and blood pressure lowering medication, if required, will be determined by the GP. All other aspects of the study appointments may be delegated to the study dietitian or nurse according to local preferences and where the study dietitian and/or nurse are willing and able to perform the procedures in the GP's opinion. The GP will be available for discussion and guidance if required by the study dietitian or nurse.

Appointment (Appt) 1 (Week -2): Screening

- Review and discuss study participation
- Secure informed consent
- Assign study ID,
- Eligibility check performed by GP
- Record medical history and medications
- Measurement of: height, weight, waist & hip circumference & blood pressure
- Provide request form for fasting blood test and urine test to be completed prior to the baseline visit: HbA1c, glucose, urea & electrolytes, creatinine, eGFR, CaPO₄, magnesium, liver function tests, lipids, full blood count and urine sample for albuminuria
- Perform Urine pregnancy test in women of childbearing potential
- Advise patient that two week step count monitoring will be collected at next visit

Appt 2 (Week 0) Baseline

- Collect 2 weeks record of daily steps
- Measurement of weight, waist circumference, blood pressure and capillary blood glucose (measured by blood glucose meter)
- Record any changes to medications
- Record any adverse events
- Hypoglycaemic medications discontinued. If capillary blood glucose > 15mmol/L the GP will determine what actions to be taken with hypoglycaemic medications.
- Antihypertensive medications reduced or ceased only if BP <110/60

- Commence VLED phase of intervention
- Questionnaire completion: EQ-5D, Binge Eating Disorder, Beacke Physical Activity and Food Acceptability Questionnaire
- Provide 1 week supply of Optifast and instructions for ordering Optifast

Appt 3-9 (Weeks 1-13): Continue VLED

- Measurement of weight, waist circumference & blood pressure
- Capillary blood glucose measured by blood glucose meter
- Record any changes to medications
- Record any adverse events
- Continue VLED intervention
- Check participant supply of Optifast

Appt 9 (Week 13) - Food reintroduction

- Begin structured food reintroduction (Step 1)
- Provide request form for non-fasting blood test to be completed within 2 days of appointment: HbA1c
- Measurement of weight, waist circumference & blood pressure

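### Questionnaires are completed at the end of Appts 2, 9 and 20, so uncontrolled change scores may carry same-visit feedback, instruction and expectation that an earlier slot would avoid

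*Protocol*

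**What the plan says.** Section 4.3.8 of the Protocol covers three self-reported instruments (EQ-5D, Binge Eating, Food Acceptability), given electronically at Appt 2, Appt 9 and Appt 20. It then sets their place within the visit: "Questionnaires will be self-completed at the end of the specific appointment".

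Other sections show what else happens at those visits:

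- Section 4.3.2: "Weight will be measured at all appointments".
- Section 4.3.6: "Capillary blood glucose will be measured at all appointments". The test is "performed by the researcher or by the patient witnessed by the researcher".
- Section 4.6, Appt 2: withdrawal of glucose-lowering drugs and the item "Commence VLED phase of intervention" belong to the same visit as the baseline questionnaires.
- Section 4.6, Appt 9: the switch to food reintroduction belongs to the same visit as the end-of-VLED questionnaires.
- Appendix A ticks weight, capillary glucose and the questionnaires at all three visits.

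The Baecke questionnaire is described in Section 4.3.7, which does not fix its place within the visit, but it shares one line with the other three in the visit lists of Section 4.6.

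**The concern.** Self-reported outcomes are usually collected before a participant is measured, told results or counselled, so that the answers reflect how the person arrived and not how the visit went. This protocol prescribes the opposite order. Because it is an instruction for data collection, no later analysis plan can undo it.

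Three features of the trial give the order some weight. The design follows only the active arm of the UK trial (Section 3), so no concurrent group shares the same influence. Section 4.5.2 defines the secondary outcomes as changes, so the Appt 2 score enters every comparison. Participants' attitudes to the VLED programme are the only secondary objective in the Summary and Synopsis, and quality of life, eating behaviour and attitudes are all secondary endpoints in Section 2.

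**Working it through.** The protocol gives no SD, expected change or size of bias for any questionnaire, so there is no figure to reproduce. The check is a comparison of sections followed by a short argument.

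**Step 1: what precedes the forms.** The sentence in Section 4.3.8 puts the forms at the end of the visit. Measurements required at that visit therefore come before them.

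| Visit | Measured that day | Other events of the visit |
|---|---|---|
| Appt 2, week 0 | weight, capillary glucose | glucose-lowering drugs stopped; VLED phase started |
| Appt 9, week 13 | weight, capillary glucose | food reintroduction started |
| Appt 20, week 52 | weight, capillary glucose | end of core period |

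The Appt 20 list in Section 4.6 omits capillary glucose, but Section 4.3.6 and Appendix A both require it. No section places the forms earlier in a visit.

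**Step 2: who is present.** The Synopsis has practice nurses or dietitians delivering the intervention. Section 4.6 lets the same staff run most of each appointment, and Appendix A assigns them the measurements. Where delivery is by telehealth, the person at the practice may be someone else.

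**Step 3: whether the influence cancels.** Write the recorded score at visit t as true score plus same-visit influence, Y(t) = T(t) + b(t). The change from baseline is then

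Y(t) − Y(0) = [T(t) − T(0)] + [b(t) − b(0)].

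The second bracket vanishes only if b(t) = b(0). The table shows that the content of the visit differs: stopping drugs and starting a strict diet at Appt 2, a change of phase at Appt 9, the closing measurements at Appt 20. Equality is therefore not assured. In a controlled trial with the same order in both arms, part of the bracket could be removed by the comparison between arms. Here nothing removes it.

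**Step 4: direction.** If starting the diet makes participants apprehensive and lowers the baseline score, b(0) < 0 and improvement looks larger. If it makes them hopeful, b(0) > 0 and improvement looks smaller. The protocol gives no basis for choosing between these.

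**Step 5: scope.** Three instruments × 3 visits × 250 participants = 2,250 forms at most. With Baecke it is 4 × 3 × 250 = 3,000. These count the forms affected. They do not measure bias.

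**The case against.** The strongest reply is that moving the forms removes only part of the feedback. Participants are weighed and glucose-tested at weeks 1, 3, 5, 7, 9 and 11 before Appt 9, and at week 49 before Appt 20. They arrive knowing most of their progress, and a new order withholds only the last 13 − 11 = 2 weeks or 52 − 49 = 3 weeks of it. This stands. It limits the gain at Appts 9 and 20, though much less at Appt 2, where the drug withdrawal and the start of the diet belong to that same day.

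A reader might infer that the baseline is not a pre-intervention state. The protocol does not support that. The Optifast supply is listed after the questionnaires at Appt 2, and drugs are stopped at that same visit, so there has been essentially no time on the diet or off treatment. What remains is instruction and expectation, and some expectation already exists from the consent discussion at Appt 1, two weeks before.

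A reader might also infer that the order exaggerates benefit in those who lose weight. The protocol offers no figure for this and describes no analysis of questionnaire scores by response.

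Three further limits stand:

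- Nothing says that every reading is told to the participant. Section 4.3.6 allows either party to do the glucose test, and Section 5 provides for discussion of results that may pose a risk to health.
- The HbA1c of Appts 9 and 20 is drawn within two days after the visit (Section 4.4), so that visit's remission result is not part of the feedback.
- The lists in Section 4.6 are not declared chronological. Appt 9, for example, lists the start of food reintroduction ahead of weighing. The order rests on the sentence in Section 4.3.8 alone.

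A constant order across visits does favour comparability, but only for influences that are themselves constant.

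**Conclusion.** The point holds as a minor improvement. The protocol expressly places the questionnaires after the day's weight and glucose measurements and at the end of the visit. At Appt 2 that is the visit at which drugs are stopped and the VLED phase starts. In a single-arm study relying on within-person change, the answers may be coloured by same-visit feedback, instruction and expectation that differ between visits, with the baseline reference most exposed.

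The wording must stay at *may be*. Size and direction cannot be derived from the document, and feedback from earlier visits would remain under any order. The conclusion assumes that at least some participants learn their readings or receive counselling before they fill in the forms, which the protocol permits but does not state for every case. The primary endpoint, HbA1c with medication status, is unaffected, and there is no internal contradiction on this point.

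**What to change.** In Section 4.3.8, replace the timing sentence with one such as: *At Appts 2, 9 and 20 participants fill in the questionnaires electronically at the start of the visit, before that visit's measurements, results, medication changes and consultation.* State the same order for the Baecke questionnaire in Section 4.3.7, and move the questionnaire item to the top of the three visit lists in Section 4.6.

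This needs no new form, visit or participant, and leaves all clinical procedures as they are. The small cost is practical: each practice must give participants access to the electronic forms on arrival, and the protocol does not yet describe a device or link for that.

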4.4 Laboratory Tests

Blood and urine laboratory tests will be performed as per Table 1 below. Laboratory services will be supplied by Douglas Hanly Moir (DHM) commercial laboratories. At each appointment where a pathology test is to be performed, the participant will be provided with a DHM request form to be completed within two days of the appointment. The dietitian/nurse will check pathology results online and ensure that all participants have completed requisite pathology tests after the appointment. The GP will review all pathology results within a week of reporting and a signed copy of the pathology results will be retained in the participant file. Screening pathology test results will be reviewed and signed by the GP prior to appointment 2/Baseline and commencement of VLED.

Table 1: laboratory tests

Time	Tests	Fasting (yes/No)
Appt 1 (Screening)	HbA1c Glucose urea & electrolytes creatinine eGFR Ca, PO4 magnesium liver function tests lipids full blood count Microalbuminuria	Yes
Appt 9 (End of VLED) Appt 13 (Week 25) Appt 16 (Week 37)	HbA1c	No
Appt 20 (Week 52)	HbA1c Glucose	Yes

	urea & electrolytes creatinine eGFR lipids, Liver function tests Microalbuminuria	
--	--	--

4.5 Outcome measurements

• 4.5.1 Primary Outcome Measure

The study primary outcome measurements are:

- reversal of diabetes (HbA1c <6.5% (48mmol/mol), off treatment for at least 2 months at 1 year (52wks)

• 4.5.2 Secondary Outcome Measure

Change in:

- Weight
- Quality of Life measured by EQ-5D
- Impact of VLED on eating behaviours measured by Binge Eating Score,
- VLED acceptability measured by Food Acceptability Questionnaire
- Physical Activity measured by the Baecke physical activity questionnaire and where available step count

Serum Lipids

Change in medications

HbA1c

lipids

LFTs

Renal function

and questionnaire scores.

The remaining outcome measurements will be collected at baseline and repeated at Appt 9 (End of VLED) and Appt 20 (Week 52). Subject to funding, these measurements will be repeated at 2 years and then every 12 months up to 5 years.

4.6 Study schedule

Eligibility for the study and reintroduction of blood glucose lowering and blood pressure lowering medication, if required, will be determined by the GP. All other aspects of the study appointments may be delegated to the study dietitian or nurse according to local preferences and where the study dietitian and/or nurse are willing and able to perform the procedures in the GP's opinion. The GP will be available for discussion and guidance if required by the study dietitian or nurse.

Appointment (Appt) 1 (Week -2): Screening

- Review and discuss study participation
- Secure informed consent
- Assign study ID,
- Eligibility check performed by GP
- Record medical history and medications
- Measurement of: height, weight, waist & hip circumference & blood pressure
- Provide request form for fasting blood test and urine test to be completed prior to the baseline visit: HbA1c, glucose, urea & electrolytes, creatinine, eGFR, CaPO₄, magnesium, liver function tests, lipids, full blood count and urine sample for albuminuria
- Perform Urine pregnancy test in women of childbearing potential
- Advise patient that two week step count monitoring will be collected at next visit

Appt 2 (Week 0) Baseline

- Collect 2 weeks record of daily steps
- Measurement of weight, waist circumference, blood pressure and capillary blood glucose (measured by blood glucose meter)
- Record any changes to medications
- Record any adverse events
- Hypoglycaemic medications discontinued. If capillary blood glucose > 15mmol/L the GP will determine what actions to be taken with hypoglycaemic medications.
- Antihypertensive medications reduced or ceased only if BP <110/60

- Commence VLED phase of intervention
- Questionnaire completion: EQ-5D, Binge Eating Disorder, Beacke Physical Activity and Food Acceptability Questionnaire
- Provide 1 week supply of Optifast and instructions for ordering Optifast

Appt 3-9 (Weeks 1-13): Continue VLED

- Measurement of weight, waist circumference & blood pressure
- Capillary blood glucose measured by blood glucose meter
- Record any changes to medications
- Record any adverse events
- Continue VLED intervention
- Check participant supply of Optifast

Appt 9 (Week 13) - Food reintroduction

- Begin structured food reintroduction (Step 1)
- Provide request form for non-fasting blood test to be completed within 2 days of appointment: HbA1c
- Measurement of weight, waist circumference & blood pressure
- Capillary blood glucose measured by blood glucose meter
- Record any changes to medications
- Record any adverse events
- Collect two week record of daily steps
- Questionnaire completion: EQ-5D, Binge Eating Disorder, Beacke Physical Activity and Food Acceptability Questionnaire

Appt 10 & 11 (Weeks 15-21) - Continue Food reintroduction

- Measurement of weight, waist circumference & blood pressure
- Capillary blood glucose measured by blood glucose meter
- Record any changes to medications
- Record any adverse events
- Continue structured food reintroduction (Step 2 & 3)

Appt 12-19 (Weeks 21-51) - Weight Maintenance

- Measurement of weight, waist circumference & blood pressure
- Capillary blood glucose measured by blood glucose meter
- Record any changes to medications
- Record any adverse events
- Behavioural weight loss maintenance intervention

Appointment 20 (Week 52) – End of Core Period

- Measurement of: height, weight, waist & hip circumference & blood pressure Provide request form for fasting blood test and urine test to be completed within 2 days of appointment: HbA1c, glucose, urea & electrolytes, eGFR, LFTs, lipids, urine for albuminuria
- Record any changes to medications
- Record any adverse events
- Collect 2 week record of daily steps
- Questionnaire completion: EQ-5D, Binge Eating Disorder, Baecke Physical Activity and Food Acceptability Questionnaire

5. ASSESSMENT OF SAFETY

Given the nature of the intervention there is very low likelihood of safety concerns. Patients will be closely monitored throughout the study with review appointments 2 weekly during the VLED and Food Reintroduction phases of the study and then monthly until week 52.

At each appointment blood pressure and postural hypotension will be monitored and antihypertensive therapy reduced, withdrawn or reintroduced if necessary, by the GP as described in section 4.2.2. Similarly, glycaemia will be monitored throughout the study as described in section 4.2.2 and appropriate treatment provided by the GP.

Any observations/results which may pose a risk to health will be discussed with the patient and their GP.

5.1 Adverse Event Monitoring

Adverse events

Adverse events are defined as any new medical event or worsening of an existing condition (including a clinically significant laboratory result) with onset after the signing of consent, whether or not the adverse event is deemed related to the study procedures. Participants will be questioned regarding the onset of any adverse events at each appointment in a non leading way (e.g how are you feeling). Participants will also be encouraged at the start of the study to spontaneously report any changes they notice while on the study. The following information will be recorded:

Adverse event term

Note: This should be a diagnosis of the event based on signs, symptoms, and/or other clinical information. In the absence of a diagnosis, the individual signs/symptoms should be documented

- Start date
- Status (resolved/recovered, resolving/recovering, not resolved/recovered, resolved/recovered with sequelae)
- End Date
- Seriousness (serious or not serious)
- Severity (mild, moderate or severe based on impact to daily functioning)
- Relationship to study treatment (definitely related, likely related, possibly related, unlikely related, not related)
- Treatment required (medication, other, none)
- Action taken with study treatment (no change in study treatment, study treatment modified, study treatment stopped)

The adverse events information may be collected and recorded by the dietitian/nurse. If the dietitian/nurse is unsure regarding relatedness and action to be taken with study procedures, they must consult the GP. If the adverse event requires treatment, this must be prescribed by the GP or another appropriately qualified health care professional.

Glycaemia and blood pressure adverse events

Hyper- and hypoglycaemia and low and high blood pressure will be recorded as adverse events using the criteria below:

Hyperglycaemia

Capillary blood glucose >15 mmol/L or HbA1c >9% or >1% change in HbA1c from previous measurement

Hypoglycaemia

Capillary blood glucose < 4 mmol/L

Low blood pressure

Systolic < 110 or diastolic <60

High blood pressure

Systolic >140 or diastolic > 90

Serious Adverse Events

Serious adverse events (SAE) are those which meet any of the following criteria:

- Results in death
- Is life threatening.

Note: this refers to an event in which the participant was at risk of death at the time of the event. It does not refer to an event, which hypothetically might have caused death if it were more severe.

- Hospital admission or prolonged hospital admission

Note: hospitalisation for elective treatment of a pre-existing condition that did not worsen from signing of consent is not considered an AE

- Congenital abnormality
- Permanent damage or disability

Note: The term disability means a substantial disruption of a person's ability to conduct normal life functions. This definition is not intended to include experiences of relatively minor medical significance such as uncomplicated headache, nausea, vomiting, diarrhoea, influenza, and accidental trauma (e.g. sprained ankle) which may interfere or prevent everyday life functions, but do not constitute a substantial disruption

- Other important medical event

Medical and scientific judgement should be exercised in deciding whether reporting is appropriate in other situations, such as important medical events that may not be immediately life-threatening or result in death or hospitalisation, but may jeopardise the participant, or may require medical or surgical intervention to prevent one of the other outcomes listed in the above definition. These should also be considered serious. Examples of such events are invasive or

malignant cancers, intensive treatment in an emergency room or at home for allergic bronchospasm, blood dyscrasias or convulsions that do not result in hospitalisation, or the abuse of study treatments

The Adverse Events form should be completed with the question regarding seriousness (serious or not serious) answered in the affirmative. Additional information including summary of the event should be recorded in the Serious Adverse Event form. It is the responsibility of the GP/dietitian/nurse to review all documentation (e.g. hospital progress notes, laboratory, and diagnostic reports) related to the event and record all relevant information in the SAE form. The event must be followed up and new information added until the event has resolved or there is no new information

Serious adverse event reporting

The Principal Investigator (PI) must be notified as soon as the GP/dietitian/nurse is aware of the SAE and within 24 hours of becoming aware. The PI must review the information in the SAE form and make a determination regarding relationship of the adverse event to the study treatment and expectedness of the adverse event. The PI must notify the sponsor (DNSW & ACT) of the SAE including assessment of causality. In the case of a Suspected Unexpected Serious Adverse Reaction (SUSAR) the HREC must also be notified as soon as the SUSAR is reported and within 24 hours of becoming aware. If the PI needs more information or wishes to discuss the event further the GP/dietitian/nurse must be available to discuss the event with the PI. Clinical oversight will be provided by the PI and where deemed necessary the participant and GP will be provided follow up correspondence.

Other safety reporting

In addition to any local SUSARs/ Unexpected and Related Serious Adverse Event (URSAEs) arising from the site, The Research Governance Office (RGO) is to receive all significant safety issues (SSIs) as defined below and the annual Safety Report. These will be submitted by the investigator to the local RGO on the relevant Notification forms.

SLHD RPA - Research Ethics and Governance Office - Safety Reporting

Summary of safety notifications to the HREC and RGO (therapeutic goods trials)

Type of event	Who reports	To whom	When	How
Significant Safety Issue (SSI) implemented as an Urgent Safety Measure (USM)	Sponsor	The reviewing HREC (and all investigators participating in the study).	As soon as possible and no later than 72 hours of the sponsor becoming aware of the USM	SSI Notification Form or sponsor's template
Significant Safety Issue (SSI) not implemented as an Urgent Safety Measure (USM)	Sponsor	The reviewing HREC (and all investigators participating in the study).	Within 15 days of the sponsor becoming aware of the SSI	SSI Notification Form or sponsor's template
All Significant Safety Issues (SSIs)	Principal Investigator	The Research Governance Officer (RGO) for the site where the event occurred	As soon as possible and no later than 72 hours of the PI becoming aware of the SSI	SSI Notification Form or sponsor's template
Suspected Unexpected Serious Adverse Reaction (SUSAR) events and Unanticipated Serious Adverse Device Effects (USADEs) occurring at the site	Principal Investigator	The Research Governance Officer (RGO) for the site where the event occurred	Within 72 hours of the PI becoming aware of the event	SUSAR/USADE/URSAE Notification Form
Investigator's Brochure/Addenda	Sponsor	The reviewing HREC (and all investigators participating in the study).	As and when updates are generated	Submitted with a cover sheet or as part of an annual progress/annual safety report
Annual Safety Report	Coordinating Principal Investigator or Sponsor	The reviewing HREC	Within annual progress report sent to the HREC or aligned with the safety reporting cycles of global companies	Annual Progress Report or sponsor's template

**Note: For trials where Sydney Local Health District is the sponsor, the sponsor functions should be delegated to the Co-ordinating Principal Investigator.*

